8.3.1. Screening Week -5 (Visit S1; Day -35 ± 7 days)

The screening period will begin with a screening visit that will occur approximately 5 weeks prior to randomization. Visit S1 will allow the investigator to assess the patient's preliminary eligibility. After the patient provides written informed consent (see [Section 8.1](#)), the patient will undergo the following assessments and procedures at Visit S1:

1. Demographics
2. Clinically relevant medical history
3. Confirmation of statin intolerance and completion of confirmation forms
4. Prior and concomitant medication review
5. Review of all inclusion/exclusion criteria that can be assessed at this time
6. Height (cm), and weight (kg)
7. BMI
8. Vital signs
9. Diet and exercise counseling
10. Central clinical laboratory evaluations:
 - TSH
 - Coagulation
 - Hematology, blood chemistry, and urinalysis
 - Basic fasting lipids (TC, calculated LDL-C, HDL-C, non-HDL-C, and TG)
 - HbA_{1C}
 - Serology (including HbsAg, hepatitis C virus [HCV] antibody)
 - Serum pregnancy test in women of child-bearing potential only
 - FSH when required
11. Contact IWRS to register the patient which includes entering whether the patient fits the definition of primary prevention or secondary prevention. The IWRS system will be designed to ensure correct definitions of primary and secondary prevention are applied for purposes of stratification.

Patients who meet all enrollment criteria that can be assessed at Visit S1 will be instructed to continue their allowed therapy(s) for lipid regulation and to maintain consistent diet and exercise patterns throughout the study. Patients who fail to meet any entry criterion, other than those that can be repeated, are considered to be screen failures and are not required to return for additional visits (although a patient can be seen at any time for safety reasons).

The screening period (between Visits S1 and S2) can be extended an additional 4 weeks if needed to adjust background therapy or other reasons.

Patients who are considered to be screen failures due to not meeting stability requirements for a condition or concurrent medication may be considered for rescreening after consultation with the Sponsor (or designee). These patients must be re-consented, re-registered in the IWRS, and will have a new patient ID number assigned.

8.3.2. Screening Week -4 (Visit S2; Day -28 ±3)

The single-blind run-in period for placebo begins at this visit. After the patient's eligibility is established, the patient will undergo the following assessments and procedures at Visit S2:

1. Concomitant medication review (ongoing)
2. Assess AEs, serious adverse events (SAEs), and potential clinical endpoints (starting from signing the informed consent document)
3. Physical examination (PE)
4. Vital signs
5. Diet and exercise counseling
6. Dispense single-blind placebo and ingestion of first dose. Provide dosing and storage instructions
7. IWRS Contact

8.3.3. Screening Week -1 (Visit S3; Day -7 ±3)

The patient will undergo the following assessments and procedures at Visit S3:

1. Concomitant medication review (ongoing)
2. Assess AEs, SAEs, and potential clinical endpoints (starting from signing the informed consent document)
3. 12-lead electrocardiogram (ECG)
4. Vital signs
5. Central clinical laboratory evaluations:
 - Hematology, blood chemistry, and urinalysis
 - Basic fasting lipids (TC, calculated LDL-C, HDL-C, non-HDL-C, and TG). LDL-C value must be ≥ 70 mg/dL
6. Diet and exercise counseling
7. Study drug compliance assessment

8.3.4. Week 0 (Visit T1; Day 1)

Prior to scheduling Visit T1, review the screening clinical results to determine whether the patient continues to meet lab eligibility criteria. At Visit T1, determine whether the patient was adherent with placebo treatment during the run-in period (average of $\geq 80\%$ adherence required)

and had no issues with tolerability of run-in period study medication. Patients with intolerable side effects, including but not limited to muscular skeletal pain, will be run-in failures.

If the patient has met all inclusion criteria and none of the exclusion criteria, the patient may be randomized into the double-blind treatment period. Patients who fail to meet all entry criteria after initiation of single-blind placebo run-in are considered to be run-in failures and will not be randomized.

Patients are considered randomized once all eligibility criteria are confirmed and IWRS is contacted with confirmation of patient randomization on the day of first dose.

The patient will undergo the following assessments and procedures at Day 1 (Visit T1):

1. Concomitant medication review (ongoing)
2. Assess AEs, SAEs, and potential clinical endpoints
3. Return of unused single-blind placebo and assessment of dosing adherence
4. Review inclusion/exclusion criteria to establish patient eligibility
5. Weight
6. Vital signs
7. Central clinical laboratory evaluations:
 - Coagulation in patients on vitamin K antagonists (return 3-5 days after Visit T1 for repeat coagulation). Coagulation samples for this visit may be analyzed at the central or local lab.
 - Hematology, blood chemistry, and urinalysis
 - apoB
 - hs-CRP
 - HbA_{1C}
 - Basic fasting lipids (TC, calculated LDL-C, HDL-C, non-HDL-C, and TG)
8. Urine pregnancy in women of childbearing potential only prior to randomization.
9. Diet and exercise counseling
10. IWRS contact to randomize patient and assign bottle number(s) for double-blind study drug
11. Dispense double-blind study drug and ingestion of first dose and provide dosing and storage instructions

8.3.5. Treatment Week 4 (Visit T2; Day 29 ±3 days)

Patients will undergo the following assessments and procedures at Week 4 (Visit T2):

1. Concomitant medication review (ongoing)
2. Assess AEs, SAEs, and potential clinical endpoints

3. Weight
4. Vital signs
5. Central clinical laboratory evaluations:
 - Hematology, blood chemistry, and urinalysis
 - Basic fasting lipids (TC, calculated LDL-C, HDL-C, non-HDL-C, and TG)
 - PK Sample prior to dose
6. Return of study drug; assessment and recording of dosing adherence
7. Re-dispense IMP container from Visit T1 to patient for continued dosing and provide dosing and storage instruction.

Note: If the patient discontinues at any scheduled visit after T1, or between study visits, please proceed to [Section 8.4.1](#) for detailed instructions.

8.3.6. Treatment Week 8 Phone Call (Visit T3; Day 57 ±3 days)

Patients will undergo the following assessments via telephone at Week 8 (Visit T3):

1. Concomitant medication review (ongoing)
2. Assess AEs, SAEs, and potential clinical endpoints
3. Diet and exercise counseling
4. Assessment of study drug dosing adherence

Note: If the patient discontinues at or between study visits, please proceed to [Section 8.4.1](#) for detailed instructions.

8.3.7. Treatment Week 12 (Visit T4; Day 85 ±3 days)

Patients will undergo the following assessments and procedures at Week 12 (Visit T4):

1. Concomitant medication review (ongoing)
2. Assess AEs, SAEs, and potential clinical endpoints (ongoing)
3. Weight
4. Vital signs
5. Central clinical laboratory evaluations:
 - Hematology, blood chemistry, and urinalysis
 - apoB
 - hs-CRP
 - HbA_{1C}
 - Basic fasting lipids (TC, calculated LDL-C, HDL-C, non-HDL-C, and TG)
 - PK Sample before dose

6. Diet and exercise counseling
7. Return of study drug; assessment and recording of dosing adherence
8. IWRS contact to obtain new MED ID numbers for double-blind study drug
9. Dispense double-blind study drug and provide dosing instruction

Note: If the patient discontinues at any scheduled visit after T1, or between study visits, please proceed to [Section 8.4.1](#) for detailed instructions.

8.3.8. Treatment Week 24/EOS (Visit T5; Day 169 ±7 days)

Patients will undergo the following assessments and procedures at Week 24 (Visit T5):

1. Concomitant medication review (ongoing)
2. Assess AEs, SAEs, and potential clinical endpoints (ongoing)
3. Weight
4. Vital signs
5. Central clinical laboratory evaluations:
 - Hematology, blood chemistry, and urinalysis
 - apoB
 - hs-CRP
 - HbA_{1C}
 - Basic fasting lipids (TC, calculated LDL-C, HDL-C, non-HDL-C, and TG)
 - PK Sample before dose
6. Return of study drug; assessment and recording of dosing adherence
7. IWRS contact to terminate the subject or register completion
8. Physical Exam
9. 12-Lead ECG

8.4. Early Withdrawal from Study or Treatment

Patients who withdraw from study drug prior to Week 24 (Visit T5) for any reason will be asked to continue to be followed for safety assessments, including basic fasting lipids, at clinic visit following the protocol-specified visit schedule (see [Section 8.3](#)).

Patients who temporarily withdraw from study drug prior to Week 24 (Visit T5) for any reason may restart study drug providing that 1) the patient and the investigator are in agreement regarding this course of action, 2) the patient has been off of study drug for 4 weeks or less; and 3) study drug can be started as soon as possible. For cases where the patient has been off of study drug for more than 4 weeks, the investigator must contact the medical monitor for approval prior to restarting study drug.

Patients who do not wish to continue to return to the clinic for safety assessments will be asked to participate in phone calls from the site at protocol-specified visits (see [Section 8.3](#)), or at a minimum at 24 weeks, to collect information on AEs, concomitant medications, and current health status.

The patient's decision to participate in the clinical study is voluntary. Patients may refuse to continue in the study and/or withdraw from participation in this study at any time, for any reason, specified or unspecified, and without penalty or loss of benefits to which the patient is otherwise entitled.

It is the right and duty of the Investigator to interrupt the treatment of any patient whose health or well-being may be threatened by continuation in this study. Such patients should be withdrawn from the study and should not be continued under a modified regimen.

Patients who are withdrawn from the study may not re-enter. The reasons for withdrawal from this study or treatment may include:

- Patient's withdrawal of consent
- Failure to comply with the protocol
- Lost to follow-up
- Illness, condition, or procedural complication (including AEs) affecting the patient's ability to participate or requiring prohibited medication
- The Sponsor or Investigator terminates the study
- In the Investigator's judgment, it is deemed in the best interest of the patient to discontinue his/her participation in the study
- Any other reason

If a patient is lost to follow-up, every reasonable effort must be made by the clinical site personnel to contact the patient and determine the reason for discontinuation/withdrawal. The measures taken to follow-up must be documented.

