10.2.11.3.2. Hepatic Function

Hepatic function will be monitored throughout with the clinical safety labs. More detailed investigation will occur if the safety clinical laboratory results are 3 times or more than the ULN).

If at any time after randomization a patient experiences a new ALT and/or AST $>3 \times$ ULN, the patient will undergo repeat confirmatory LFT assessment as soon as is reasonably possible, preferably within 3 to 7 days of the laboratory result becoming available.

Repeat LFT assessment will include: 1) measurement of ALT, AST, alkaline phosphatase, total and direct bilirubin, prothrombin time (PT)/international normalized ratio (INR), eosinophil count, CK, antihepatitis A virus (total), HBsAg (confirmation of screening measurement), HCV (confirmation of screening measurement), and anti-cytomegalovirus/immunoglobulin M; 2) history of concomitant medication use; 3) history of exposure to environmental chemical agents, including ethanol; and 4) query for related symptoms. Additionally, further testing such as liver ultrasound or magnetic resonance imaging (MRI) scanning may be warranted to rule out additional pathology depending on clinical presentation and should be discussed with the Sponsor personnel or the authorized Medical Monitor.

- If repeat LFT assessment confirms ALT and/or AST $>3 \times$ ULN, consideration should be given to withdrawing the patient and administering no further doses of study drug. At the investigator's discretion, study drug may be interrupted and the patient rechallenged with study drug after LFTs have returned to baseline levels.
- If repeat LFT assessment confirms ALT and/or AST $>5 \times$ ULN, patient should be withdrawn from study drug treatment, but will be asked to continue to be followed for safety using the protocol-specified visit schedule (see [Section 8.3](#)) or more frequently if deemed appropriate by the Investigator.
- If repeat LFT assessment confirms ALT and/or AST $>3 \times$ ULN in addition to any of the following, the patient should be given no further treatment with study drug, but will be asked to continue to be followed for safety using the protocol-specified visit schedule (see [Section 8.3](#)) or more frequently if deemed appropriate by the Investigator:
 - TB $>2 \times$ ULN (will be fractionated if $>2 \times$ ULN and for those with Gilbert's Disease $2 \times$ ULN conjugated (direct) bilirubin will be evaluated)

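### Protocol Section 8.4 withdraws from the study patients whose treatment is interrupted for their protection, contradicting its own follow-up rule and the specific safety rules

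*Protocol*

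**What the plan says.** Protocol Section 8.4 contains three instructions that bear on a patient whose drug is stopped or held.

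- **Off drug.** Patients who come off study drug before Week 24 "for any reason will be asked to continue to be followed for safety assessments, including basic fasting lipids" on the protocol visit schedule.
- **Temporary stop.** "Patients who temporarily withdraw from study drug prior to Week 24 (Visit T5) for any reason may restart study drug", subject to conditions on agreement and time off drug.
- **Interruption for the patient's protection.** "It is the right and duty of the Investigator to interrupt the treatment of any patient whose health or well-being may be threatened"; the sentence goes on to tie that threat to carrying on in the study. Then: "Such patients should be withdrawn from the study and should not be continued under a modified regimen". The next paragraph opens: "Patients who are withdrawn from the study may not re-enter".

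The specific safety rules take the first line, not the third. For confirmed marked transaminase elevation, Section 10.2.11.3.2 says the "patient should be withdrawn from study drug treatment, but will be asked to continue to be followed for safety using the protocol-specified visit schedule". The renal rule (10.2.11.1 and 10.2.11.3.5), the hemoglobin rule (10.2.11.1), the CK rule (10.2.11.3.3) and the triglyceride rule (10.2.12) likewise remove drug and ask for continued follow-up. The hepatic and CK rules also provide for interruption followed by rechallenge or resumption. The notes under Table 2 and Appendix 1 keep patients who are off drug on the visit schedule with basic lipids, though without apoB and hs-CRP.

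**The concern.** A patient whose drug is held because of a safety worry fits all three parts of Section 8.4 at once, and the three cannot all be followed. One site may keep the patient in follow-up; another, reading the later paragraph, may end participation. I found no statement of which text takes precedence.

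This matters because the efficacy analysis uses all randomized patients regardless of treatment received (Protocol 11.3, SAP 5.2). For that analysis an off-treatment Week 12 lipid value is a valid observation, and SAP Appendix 4 has cohorts for exactly such patients (7 and 8). A patient taken out of the study may not supply that value. In the bempedoic acid arm it is then replaced by an imputation from placebo data (SAP 18.1.3, Appendix 4). Week 24 LDL-C, second in the stepdown sequence, is handled the same way. An obtainable measurement becomes an assumption because of a drafting conflict.

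**Working it through.** The plan has no figure of its own to reproduce here. The check is a comparison of texts, followed by an illustration of size.

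**1. The texts side by side**

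| Place | Study drug | Study follow-up |
|---|---|---|
| 8.4, first paragraph | stopped, any reason | visits continue, with fasting lipids |
| 8.4, second paragraph | temporary stop, any reason; restart possible | continues |
| 8.4, interruption paragraph | interrupted for the patient's protection; no modified regimen | withdrawn from study, no re-entry |
| 10.2.11.1 and 10.2.11.3.5 (renal), 10.2.11.1 (hemoglobin), 10.2.12 (triglycerides) | stopped | continues on visit schedule |
| 10.2.11.3.2 (hepatic), 10.2.11.3.3 (CK) | stopped, or held with possible return | continues on visit schedule |
| Notes to Table 2 and Appendix 1 | stopped | visits continue, with basic lipids |

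A reason that covers every case also covers safety. The third row therefore conflicts with the two above it and with all those below.

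**2. Which data are exposed**

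The schedule notes omit apoB and hs-CRP for patients off drug, so the scheduled values at risk are LDL-C, non-HDL-C and total cholesterol at Weeks 12 and 24. Those in the stepdown sequence (LDL-C at both weeks, non-HDL-C and total cholesterol at Week 12) are imputed when missing.

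**3. How far Section 8.4.1 repairs it**

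Section 8.4.1 requires End of Study procedures for anyone who withdraws or is removed; under 8.3.8 these include fasting lipids. Whether that sample can serve as Week 12 depends on the visit windows. The window table in SAP 6.4 is broken in the available text, but by order the Week 12 window is days 72 to 127. This agrees with midpoints between scheduled visit days: (57 + 85)/2 = 71 and (85 + 169)/2 = 127. On that reading, a sample from a patient removed before day 72 does not count as Week 12, and one taken before day 128 does not count as Week 24. The text of SAP 6.3 on early termination data is not visible, so this cannot be settled fully.

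**4. Illustration of size (all rates and effects assumed)**

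Let d be the share of patients withdrawn under this sentence before Week 12 with no usable value, equal in both arms. The numbers randomized are 200 and 100.

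- Missing values: 200d + 100d.
- Standard error inflation: 1/√(1 − d).
- Power: Φ(δ/SE − 1.96), with SE = √(1/n_b + 1/n_p), n_b = 200(1 − d), n_p = 100(1 − d) and δ a standardized effect. This treats lost values as dropped, not imputed, so it is only a rough guide.
- Shift in the bempedoic acid mean if true off-drug values differ from the placebo-based imputation by 5 percentage points: 5d.

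| d | Missing (bempedoic acid + placebo) | SE inflation | Power, δ = 0.4 | Power, δ = 0.5 | Mean shift (points) |
|---|---|---|---|---|---|
| 0 | 0 | 1.000 | 90.4% | 98.3% | 0 |
| 1% | 2 + 1 = 3 | 1.005 | 90.1% | 98.2% | 0.05 |
| 2% | 4 + 2 = 6 | 1.010 | 89.9% | 98.1% | 0.10 |
| 5% | 10 + 5 = 15 | 1.026 | 88.9% | 97.8% | 0.25 |
| 10% | 20 + 10 = 30 | 1.054 | 87.3% | 97.2% | 0.50 |

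At δ = 1.0 power stays at about 100% throughout.

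**The case against.** The strongest answer is that the disputed paragraph is a general clause for patients for whom taking part is itself the hazard, not for every drug hold. The foreseeable stops have their own rules, and a site would usually apply those. The repeated pattern, including the SAP cohorts for observed off-treatment values, shows that continued follow-up is the intended design. This stands as a limit on scope: the documents do not show that safety-stopped patients would routinely leave the study. It does not remove the conflict, because the paragraph is worded around interrupting treatment and so applies directly to hepatic and CK holds.

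Section 8.4.1 is also a real safeguard. Besides End of Study procedures, it asks that every effort be made to complete scheduled visits, and it seeks consent to visits or calls through Week 24 even from those leaving entirely. But its encouragement to attend all visits is addressed to patients who leave by their own choice, and the contact after full withdrawal may be by telephone and does not list lipids.

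Two stronger readings are tempting and should be resisted.

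- A reader might infer that all later safety data would be lost. Section 10.2.6 follows adverse events that lead to study discontinuation to resolution or stabilization, 10.2.7.4 requires serious events to be reported until 30 days after the last dose, and 8.4.1 seeks safety contact to Week 24.
- A reader might infer that the loss would fall unequally on the arms. That is possible, but nothing in the documents supports it; Section 10.2.11.1 reports generally similar adverse event incidence across groups, headache excepted.

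**Conclusion.** The contradiction is certain and sits in current protocol text. Its consequence is conditional: where a site follows the withdrawal sentence, obtainable off-treatment lipids can go missing, and for bempedoic acid patients the stepdown endpoints rest on placebo-based imputation instead. Section 8.4.1 reduces this without removing it.

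The size is not known. The documents give no rate of safety interruption, so the 10 to 20 bempedoic acid values at 5–10% are an illustration, not an expectation. Reaching them would also require that sites apply this sentence over the specific rules and that no affected patient supplies a value in the window. The effect on power is probably small under the assumed effects. The reason to act is avoidable dependence on imputation and inconsistent conduct between sites. It is not a threat to the primary conclusion that the documents would support.

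**What to change.** Reconcile the interruption paragraph of Protocol 8.4 with the first two paragraphs of that section, with 8.4.1, and with the safety rules in 10.2.11 and 10.2.12. Stopping or interrupting study drug should be kept distinct from leaving the study throughout, and the text on continued visits and lipid sampling should be the same in every place. The encouragement in 8.4.1 to attend all visits should be worded so that it is clear whether it also covers patients removed by the investigator. When treatment is stopped, held or restarted is for the clinical team to decide; this point takes no position on it.

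The cost is amendment wording and a site reminder. No change to sample size, visits or the analysis model is needed.

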8.4.1. Procedures for Early Withdrawal

If a patient withdraws or is removed from the study for any reason, all "End of Study" procedures should be completed. Reason for withdrawal, date of the discontinuation, and date of the last dose of study drug should be recorded in the appropriate section of the eCRF.

Additionally, the discontinuation visit date must be registered in IWRS. Study drug assigned to the withdrawn patient may not be assigned to another patient.

All effort should be made to have each patient complete all study visits on schedule according to the protocol. Accommodations for early or late visits in special circumstances will be considered by the Sponsor to prevent early withdrawal. Written notice (regardless of cause) is to be provided within 48 hours of the withdrawal to the Sponsor personnel or the Medical Monitor. At the time of discontinuation, every effort should be made to ensure all relevant procedures and evaluations scheduled for the final study visit are performed.

Patients choosing to withdraw from the study early should be encouraged to return for all study scheduled clinic visits even if they are no longer taking IMP. Patients who withdraw from all aspects of the study will be asked to consent to clinical visits or phone calls for safety assessments, including AEs, concomitant medication, and current health status through Week 24 (Visit T5). Subjects who are unwilling to return for clinic visits should return for an end of study visit (Visit T5).

